1.3 Schedule of Events

The schedule of events (SOE) is presented in [Table 1](#) and [Table 2](#).

Table 1 Schedule of Events (excluding Cohort C-1)

Cycle/Period	Pre- screening	Screening	C1				C2		C3+	EOT	Safety Follow- up	Efficacy Follow- up	Survival Follow- up
Visit			D1	D8	D15	D22	D1	D15	D1	Within 7 Days After the Last Dose	30 Days After the EOT Visit	Every 12 Weeks From EOT Visit	Every 12 Weeks From EOT Visit
Visit Window (days)	--	-28 to -1	--	±1	±1	±1	±1	±1	±3	±3	±7	±14	±14
Activities													
Pre-screening informed consent ¹	X												
Main informed consent ²		X											
IDH mutational status ³	X	X								X			
Medical history and demographics ⁴	X	X											
Prior and concomitant medications and concomitant procedures ⁵		X	X	X	X	X	X	X	X	X	X	X	
Height		X											
Physical examination, vital signs, and weight ⁶		X	X	X	X	X	X	X	X	X			
ECOG performance status ⁶		X	X		X		X	X	X	X			
Ophthalmologic examination ⁷		X						X (±1 week)	Every 12 weeks (±1 week) from C4D1				
Laboratory evaluations ⁶													
Hematology ⁸		X ⁹		X	X	X	X	X	X	X	X		
Blood chemistry ¹⁰		X ⁹		X	X	X	X	X	X	X	X		
Blood amylase and lipase		X ⁹		X	X	X	X	X	X	X			
Fasting lipid panel ¹¹		X ⁹			X		X		X	X			
Coagulation indicators ¹²		X ⁹			X		X		X				
Pregnancy test ¹³		X	X				X		X	X	X		
Urinalysis ¹⁴		X ⁹					X		X	X			

Table 1 Schedule of Events (excluding Cohort C-1)

Cycle/Period	Pre-screening	Screening	C1				C2		C3+	EOT	Safety Follow-up	Efficacy Follow-up	Survival Follow-up
Visit			D1	D8	D15	D22	D1	D15	D1	Within 7 Days After the Last Dose	30 Days After the EOT Visit	Every 12 Weeks From EOT Visit	Every 12 Weeks From EOT Visit
Visit Window (days)	--	-28 to -1	--	±1	±1	±1	±1	±1	±3	±3	±7	±14	±14
Activities													
Virological screening ¹⁵		X											
HbA1C		X ⁹			X		X		X	X			
PK and PD assessments	Refer to Appendix 1												
12-lead ECG ^{6,16}	Refer to Appendix 1												
ECHO/MUGA scan		X					X		C3D1 then Day 1 of every odd cycle (ie, C5D1, C7D1, etc.) (±1 week)				
Tumor evaluation/imaging ¹⁷		X	Every 8 weeks from C1D1 during the first 24 (±1) weeks and every 12 (±2) weeks thereafter								X		
Tumor tissue for exploratory biomarker evaluation. Applies to Cohorts A, B, and D only ¹⁸		X					X±7 days		At disease progression only in dose expansion				
Blood for gene mutation analysis ¹⁹		X	Only in dose expansion; refer to Appendix 1										

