6.1.19 End of Treatment Visit

Subjects who have completed the study or have discontinued study treatment will be asked to return to the investigational site to receive safety examinations and assessments within 7 (± 3) days after the last dose of study drug.

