15 APPENDICES

APPENDIX 1 PK, PD, AND BIOMARKER ASSESSMENTS (EXCLUDING COHORT C-1)

Study Day	Time Relative to Dosing	Study Drug Intake	Blood Samples for PK	Blood Samples for 2-HG	Blood Samples for Gene Mutation Analysis	ECG
Screening				X	X ²	X
C1D1	Predose ¹		X	X		X ⁴
	0 h	X				
	0.5 h (± 2 min)		X			
	1 h (± 5 min)		X			X ⁴
	2 h (± 10 min)		X			X ⁴
	3 h (± 10 min)		X			
	4 h (± 15 min)		X			X ⁴
	6 h (± 15 min)		X			
	8 h (± 15 min)		X			
C1D2	Predose ¹		X	X		
	0h	X				
C1D8	Predose ¹		X	X		
	0 h	X				
C1D15	Predose ¹		X	X		
	0 h	X				
C1D22	Predose ¹		X	X		
	0 h	X				
C2D1	Predose ¹		X	X	X ³	X ⁴
	0 h	X				
	0.5 h (± 2 min)		X			
	1 h (± 5 min)		X			X ⁴
	2 h (± 10 min)		X			X ⁴
	3 h (± 10 min)		X			
	4 h (± 15 min)		X			X ⁴
	6 h (± 15 min)		X			
	8 h (± 15 min)		X			
C2D2	Predose ¹		X			
	0 h	X				
C2D15	Predose ¹		X	X		
	0 h	X				
C3D1	Predose ¹		X	X	X ³	X
	0 h	X				
C5D1	Predose ¹		X	X	X ³	X
	0 h	X				

Study Day	Time Relative to Dosing	Study Drug Intake	Blood Samples for PK	Blood Samples for 2-HG	Blood Samples for Gene Mutation Analysis	ECG
C7D1	Predose ¹		X	X	X ³	X
	0 h	X				
C10D1 and every 3 cycles thereafter	Predose ¹		X	X	X ³	X
	0 h	X				
EOT (Within 7 days after the last dose)	Anytime			X	X ³	
Safety Follow-up period (30 days after EOT Visit)	Anytime					X

2-HG = 2-hydroxyglutaric acid; CxDx = Cycle X Day X; ECG = electrocardiogram; EOT = end of treatment; PD = pharmacodynamics; PK = pharmacokinetics.

- ¹ Should be performed within 30 minutes before the dosing on that day and approximately 24 hours (±60 minutes) after dosing on the previous day (ie, Day 1 of Cycle 1 or 2).
- ² Whole blood will be collected for potential analysis of CCI at baseline in dose escalation and dose expansion. Samples collected in dose expansion will also be used for analysis of gene mutation abundance.
- ³ Whole blood will be collected in dose expansion only for analysis of gene mutation abundance, such as *IDH1*, *IDH2* (R140 and R172), CCI, etc.
- ⁴ To be performed in triplicate with intervals of approximately 5 minutes.

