2.2. Study Design

[figure not shown]
This is a phase 1, open-label, multicenter study to evaluate the safety and tolerability of HMPL 306 administered orally (PO) in treatment of patients with locally advanced or metastatic solid tumors with IDH mutation. The study consists of 2 parts: Part 1 (dose escalation) and Part 2 (dose expansion). Only part 1 included in this analysis plan.

The first part of the study is dose escalation where cohorts of patients will receive ascending oral doses of HMPL-306 to determine maximum tolerated dose (MTD) and/or the recommended phase 2 dose (RP2D). The modified toxicity probability interval-2 (mTPI-2) (Yang et al, 2015) design will be utilized. The mTPI-2 method uses a Bayesian framework and a hierarchical model to compute the dose escalation based on the interval between the toxicity rate of each dose level and target probability (Guo et al, 2017). This study is designed targeting a dose-limiting toxicity (DLT) rate of 25% with an equivalence interval of 20% to 30%.

A cycle of study treatment is defined as 28 days of continuous daily dosing, according to the cohort and dose level. At the starting dose, patients will be administered HMPL-306 at [REDACTED] mg PO, QD, and the dose will escalate successively according to the sequence of [REDACTED] mg QD, [REDACTED] mg QD, [REDACTED] mg QD, [REDACTED] mg QD, [REDACTED] mg QD, [REDACTED] mg QD, and [REDACTED] mg QD.

The overall study schema of part 1 is presented in Figure 1

Figure 1 Study Schema

Subjects who complete the DLT assessment window and are deemed by the investigator to be benefiting from HMPL-306 treatment will be allowed to continue treatment until disease progression, intolerable toxicity, at the investigator's discretion that the subject can no longer

benefit from the study treatment, withdrawal of consent, lost to follow-up, the end of study, or death, whichever comes first.

Safety Follow-up

Subjects who have completed the study treatment will be evaluated for safety 30 days (± 7) days following the EOT visit for study drug-related AEs until resolution and SAEs until resolution regardless of relationship to study treatment.

Efficacy Follow-up

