4.1.3. Treatment Period

Unless otherwise specified, the treatment period is defined as the period prior to or on the date of first administration of study drug to 30+7 days (7-day window only replies to parameters collected by visit) after the date of last administration of study drug or prior to the start of a subsequent anti-tumor therapy (whichever comes first). For safety data, only the assessments/events collected during the treatment period will be summarized.

The worst post baseline is defined as the worst assessments/events during the treatment period including both scheduled and non-scheduled visit.

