4.4.1. Adverse Events (AEs)

All AEs will be coded from verbatim text to preferred term (PTs) and grouped by system organ class (SOC) using the Medical Dictionary for Regulatory Activities (MedDRA) version 27.1. AEs will be graded by investigator according to NCI CTCAE v5.0. Missing severity grade will not be imputed.

An AE is considered a TEAE:

(i) If one of the criteria is met:

1. If the onset date is on or after the start of study treatment until 30 days after the last dose or prior to the start of a subsequent anti-tumor therapy (whichever comes first), or if the onset date is missing; or
2. If the AE has an onset date before the start of study treatment, but worsened in severity after the study drug administration (i.e. SAE start date is on or after the start of study treatment until 30 days after the last dose or prior to the start of a subsequent anti-tumor therapy (whichever comes first));

(ii) Beyond 30 days after the last dose or after the start of a subsequent anti-tumor therapy (whichever comes first), treatment-related SAEs will also be considered as TEAEs.

Investigator assessed AEs causality to study drug will be classified as "Related" and "Not Related". An AE with a missing causality will be classified as "Related" to study drug.

Other AE variables include drug-related AEs, COVID-19 related AEs, AEs leading to study drug modifications (i.e. dose interruption, dose reduction, or study drug withdrawal), AEs leading to death, and SAEs.

For AEs which are not on-going, duration of AE (days) is defined as AE end date – AE start date +1; for on-going AEs, the end date will be listed as ‘Ongoing’.

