5.2.11. Safety Analyses

Safety data during the treatment period will be summarized. Treatment period is defined as the duration from the date of the first study drug administration until 30+7 days (7-day window only applies to parameters collected by visit) or prior to the start of a subsequent anti-tumor therapy (whichever comes first) after last study drug administration.

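### The SAP's by-visit safety window closes 37 days after last dose, but a Safety Follow-up visit on schedule can fall as late as day 47, so some follow-up ECGs and laboratory results are listed but not summarised

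*SAP*

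**What the plan says.** SAP 4.1.3 closes the treatment period at "30+7 days (7-day window only replies to parameters collected by visit) after the date of last administration of study drug", or at the start of subsequent anti-tumor therapy if that comes first. It then states: "For safety data, only the assessments/events collected during the treatment period will be summarized". SAP 4.4 gives the same 30+7-day limit, and SAP 5.2.11 opens with "Safety data during the treatment period will be summarized" and repeats it. No laboratory or ECG section of the SAP sets a different window.

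The visit that supplies the last scheduled safety data is timed differently. SAP 2.2 reads "Subjects who have completed the study treatment will be evaluated for safety 30 days" (±7) after the EOT visit. Protocol 6.1.20 and Table 1 say the same, and Appendix 1 labels the row "Safety Follow-up period (30 days after EOT Visit". The EOT visit itself is "Within 7 Days After the Last Dose" in Table 1, with a ±3-day window. Protocol 6.1.19 agrees: patients return "to receive safety examinations and assessments within 7" (±3) days of the last dose.

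Table 1 schedules hematology and blood chemistry at both EOT and Safety Follow-up. Appendix 1 schedules an ECG at Safety Follow-up and none at EOT.

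**The concern.** The two clocks start on different days. The SAP counts 30+7 days from last dose, while the visit is counted 30±7 days from EOT. The seven extra days match the visit's own tolerance but leave out the interval between last dose and EOT. A visit made exactly as scheduled can then fall outside the period that the SAP will summarise.

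ECGs and laboratory abnormalities are part of the Part 1 primary safety endpoint, and protocol Table 3 names QTcF prolongation as a potential risk to be monitored throughout the study. SAP 4.1.3 defines the worst post-baseline value within this same period. That value feeds the laboratory and ECG shift tables, and SAP 5.2.11.5 limits the potentially-clinically-significant ECG counts to the same period. The cohorts are small: 27 to 36 subjects over eight dose levels average 27/8 = 3.4 to 36/8 = 4.5 per level, so one omitted patient can visibly change a cohort's table.

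**Working it through.** **Inputs**

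- Window end for by-visit parameters: 30+7 days after last dose (SAP 4.1.3, 4.4, 5.2.11).
- EOT visit: within 7 (±3) days after last dose (Protocol Table 1 and 6.1.19).
- Safety Follow-up visit: 30 (±7) days after EOT (SAP 2.2; Protocol Table 1 and 6.1.20).

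**The plan's own figure.** Window end = 30 + 7 = day 37. If the visit were timed from last dose it would fall on days 30−7 = 23 to 30+7 = 37, which the window covers exactly. The same holds if EOT is on the day of last dose.

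**As scheduled.** Let e be the EOT day, counted from last dose. The visit falls on days e+23 to e+37, which is 15 permitted days. The number of those days after day 37 is e.

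| EOT day e | Permitted visit days | Target day | Days after day 37 |
|---|---|---|---|
| 0 | 23–37 | 30 | 0 of 15 |
| 1 | 24–38 | 31 | 1 of 15 (7%) |
| 4 | 27–41 | 34 | 4 of 15 (27%) |
| 7 | 30–44 | 37 | 7 of 15 (47%) |
| 10 | 33–47 | 40 | 10 of 15 (67%) |

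Latest compliant visit: 7 + 3 + 30 + 7 = day 47, ten days past the window. Without the +3 allowance for EOT it is 7 + 30 + 7 = day 44.

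Over all whole-day combinations:

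- EOT days 0–10: (0+1+…+10)/(11×15) = 55/165 = 33%.
- EOT days 0–7: (0+1+…+7)/(8×15) = 28/120 = 23%.

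These are shares of permitted day combinations. They ignore the cut-off at new anti-tumor therapy, which would exclude some of the same visits under either rule.

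**Which data are affected.** The EOT visit is at most day 10, well inside 37 days, so its hematology and chemistry results are summarised whatever happens later. With no EOT ECG scheduled, a patient whose Safety Follow-up visit falls on days 38 to 47 has no scheduled post-treatment ECG in any summary table.

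**The case against.** **The data are not lost.** A reader might infer that these results disappear from the report. They do not: SAP 5.2.11.4 and 5.2.11.5 list all laboratory and all ECG data, and at this sample size the listings can be read patient by patient. This stands, and it confines the point to the summary tables.

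**The laboratory effect is small.** An EOT sample is already summarised, so only a second post-treatment value is excluded. This also stands. Unscheduled ECGs are allowed and count if they fall inside the window, but they do not replace a scheduled assessment.

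**Late treatment-related SAEs.** A reader might infer that the treatment-period restriction also removes related SAEs that start more than 30 days after last dose. The documents do not support this. SAP 4.4.1 has a specific rule that such "treatment-related SAEs will also be considered as TEAEs", and SAP 5.2.11.2 tabulates TEAEs and serious TEAEs as so defined. The period definition in 4.1.3 also yields to provisions made elsewhere.

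**Intent and preference.** The SAP never says that the seven days are there to capture the follow-up visit, and a longer by-visit period would widen the gap to the 30-day AE window from 7 to 17 days. It is also not shown that any patient's worst value would first appear after day 37. These remarks are fair, but the seven days are given only to parameters collected by visit, and SAP 2.2 itself times that visit from EOT. The mismatch remains whatever was intended.

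**Protocol version.** The SAP follows Amendment 3, while the EOT timing and the ECG schedule used here are from Amendment 2. Day 47 and the absence of an EOT ECG are therefore unconfirmed for the governing version. The difference in anchor is not in doubt, because it lies within the SAP: any EOT visit at least one day after last dose lets a compliant follow-up visit fall outside. Protocol Appendix 2 times follow-up from termination of treatment, which would fit 37 days, but it covers only Cohort C-1, which enrolled no one.

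**Conclusion.** The point holds as an inconsistency of anchor inside the SAP. Its by-visit summaries stop at day 37, and a Safety Follow-up visit on schedule can come up to ten days later. The consequence is incomplete summary tables, chiefly for the follow-up ECG, with the listings intact.

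The 47% (EOT on day 7) and 33% (EOT days 0–10) describe how much of the permitted timing lies outside the window. They should not be read as the fraction of patients affected: the documents give no distribution of visit dates, and patients who start new therapy earlier are cut off in any case. The 30-day AE-onset window is not in question, since the protocol collects AEs over the same period. The day-47 figure and the ECG schedule rest on Amendment 2; the anchor mismatch does not.

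**What to change.** In SAP 4.1.3, 4.4 and 5.2.11, define the period for by-visit parameters as running through the Safety Follow-up visit: EOT visit date + 30 + 7 days, at most 47 days after last dose, or the start of subsequent anti-tumor therapy if earlier. Keep 30 days after last dose for AE onset. Check the EOT timing and the ECG schedule against Amendment 3 before fixing the 47-day cap.

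The cost is the wording of three SAP sections and one constant in the derivation code. The assessments are already scheduled and listed, so no new data are needed.

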4.2. Efficacy Endpoints

4.2.1. Secondary Endpoints

4.2.1.1. Best Overall Response

BOR will be determined using time point responses (TPRs) up until the last evaluable TPR prior to or on the date of (i) disease progression as defined by RECIST Version 1.1 (Eisenhauer et al., 2009) or RANO criteria for glioma patients, or death; or (ii) withdrawal of consent or lost to follow-up; or (iii) receiving subsequent anti-cancer medications, whichever is earlier.

The timing of an overall TPR will always be derived based on scan dates, not response assessment dates. For a scheduled tumor scan assessment, it is expected that there may be a variation for the actual timing of scans among target, non-target, and new lesions. In assigning a date for the overall response assessment at a visit, the earliest date collected at that visit will be used. Within a grouped timepoint, if there are multiple assessments on different dates for the same target lesions, the last assessment will be used.

BOR as defined by RECIST:

A patient's BOR will be determined based on [Table 2](#).

There are two ways of assigning BOR for a patient when the minimum interval for confirmation of CR and PR is not satisfied or if there are no confirmatory scans for CR and PR:

- Adding two more response categories as: unconfirmed CR, unconfirmed PR;
- Assigning BOR as SD, that is, both the unconfirmed CR and unconfirmed PR will be SD.

Both ways of assigning BOR will be implemented.

The number and percentage of patients in each category of derived BOR (Confirmed CR, Confirmed PR, SD, PD, or NE) will be summarized.

Table 2 Best Overall Response When Confirmation of CR and PR are Required

First TPR	Second TPR	Best overall response*^ for ORR	Best Overall Response for ORR _{UNCONFIRMED}
CR	CR	CR	CR
CR	PR	SD [b] or PD	Unconfirmed CR
CR	SD	SD [b] or PD	Unconfirmed CR
CR	PD	SD [b] or PD	Unconfirmed CR
CR	NE or NA	SD [c] or NE or NA	Unconfirmed CR
PR	CR	PR	Unconfirmed CR
PR	PR	PR	PR
PR	SD	SD [d]	Unconfirmed PR
PR	PD	SD [b] or PD	Unconfirmed PR
PR	NE or NA	SD [c] or NE or NA	Unconfirmed PR
NE	NE	NE	NE
NE	CR	SD	Unconfirmed CR
NE	PR	SD	Unconfirmed PR

NE	SD	SD	SD
NE or NA	PD	PD	PD
SD	PD	SD [b] or PD	SD [b] or PD
SD	CR	SD	SD
SD	PR	SD	SD
SD	SD	SD	SD
SD	NE or NA	SD [c] or NE or NA	SD [c] or NE
PD	No further evaluation	PD	PD

CR = Complete Response; NE = Not Evaluable; NA = Not Available; ORR = Objective Response Rate; PD = Progressive Disease; PR = Partial Response; SD = Stable Disease.

[a]The minimum interval for confirmation of CR and PR is 4 weeks.

[b]Best response will be SD if the first time point overall response is after 49 days on study. Otherwise, the best response will be PD.

[c]Best response will be SD if the first time point overall response if after 49 days on study. Otherwise, the best response will be NE.

[d]Best response will be SD provided the criteria for PD have not been met from the first to second assessment.

* A best overall response of SD can only be made after the patient is on study for a minimum of 49 days (counted from Cycle 1 Day 1). If the patient is on study for less than 49 days, any tumor assessment indicating stable disease before this time period will have a best response of NE unless PD is identified.

^ Subsequent documentation of a CR may provide confirmation of a previously identified CR even with an intervening NE (e.g., CR NE CR). Subsequent documentation of a PR may provide confirmation of a previously identified PR even with an intervening NE or SD (e.g., PR NE PR or PR SD PR). However, only one (1) intervening NE or SD will be allowed between CRs or PRs for confirmation. Note: in the following scenario, PR SD NE PR, the second PR is not a confirmation of the first PR.

BOR as defined by RANO (for glioma patients):

The BOR was the best response among all the available time point responses (TPRs), the category of TPRs includes CR, PR, MR, SD, PD, and NE, and the order of the response is CR>PR>MR>SD>PD>NE. The hierarchical algorithm of deriving BOR category is detailed below.

- CR = at least one determination of CR. For example, a patient with 3 TPRs being CR, MR, and SD, then the BOR for this patient is CR.
- PR = at least two consecutive determinations of PR at least 4 weeks apart and before first documented PD or PR being the first response and being sustained for at least 4 weeks. For the consecutive determination of PR, the subsequent documentation of a PR may provide confirmation of a previously identified PR even with an intervening NE, SD, or MR (e.g., PR NE PR, PR SD PR, or PR MR PR). However, only one (1) intervening NE, SD, or MR will be allowed between PRs for confirmation, that is, in the following scenario, PR SD NE PR, the second PR is not a confirmation of the first PR. For PR being the first response, one intervening NE can be allowed before the response of PR, that is, in the response sequence of NE PR, the PR can also be considered as the first reported response.

For example, (i) consecutive determinations of PR: a patient with 3 TPRs being PR, PR, and SD, and the duration between the two PRs is 6 weeks, then the BOR for this patient is PR; (ii) PR being the first response: a patient with 3 TPRs being PR, MR, and SD, and the duration between first dose date and the PR is 5 weeks, then the BOR for this patient is PR; a patient

with 2 TPRs being SD, PR, then the PR will be downgraded to MR, hence, the BOR will be MR.

- MR = at least one determination of MR or not qualifying for PR criteria given that there are TPRs being PR. For example, (i) a patient with 3 TPRs being MR, SD, and SD, then the BOR for this patient is MR; (ii) a patient with 2 TPRs being SD and PR, however, the PR did not meet the criteria for BOR being PR, then the PR will be downgraded to MR, hence, the BOR for this patient will be MR.
- SD = at least one SD assessment or better before first documented PD (and not qualifying for CR, PR, MR, and PD). For example, a patient with 3 TPRs being SD, NE, and PD, then the BOR for this patient is SD.
- PD = PD after the first dose date and not qualifying for CR, PR, MR, and SD.
- NE = all other cases but patients are evaluable

The number and percentage of patients in each category of derived BOR (CR, PR, MR, SD, PD, or NE) will be summarized.

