Despite the lack of clear treatment options for these patients, there is emerging data for IDH inhibitors for the treatment of patients with chondrosarcomas harboring IDH mutations. An ongoing Phase 1 study of AG-120 (IDH1 inhibitor) enrolled 21 patients with locally advanced or metastatic chondrosarcoma harboring mIDH1. Among the 21 patients enrolled, 11 patients (52.4%) received prior systemic therapy. Patients achieved a median PFS of 5.6 months (95% CI, 1.9 to 7.4 months); the PFS rate at 6 months was 39.5%, and 11 patients (52.4%) experienced stable disease. AG 120 also showed minimal toxicity and durable disease control (Tap 2020).

Cohort C: Glioma

This study plans to enroll subjects with recurrent Grade 2 gliomas that are not a candidate for clinical resection.

Isocitrate dehydrogenase mutations are highly prevalent in patients with low-grade glioma, occurring in up to approximately 80% of all cases. However, given the toxicities associated with

chemotherapy and radiation, there remains a significant unmet need to improve treatment options for patients living with IDH mutant gliomas. Standard treatment consists of resection, followed by radiation and chemotherapy. Treatment is not curative and current therapy is associated with short- and long-term toxicity. Upon recurrence, due to heterogeneity of disease, there is no one standard treatment regimen. Both EU and US guidelines recommend repeat surgery, alkylating chemotherapy re-irradiation, or experimental therapy ([Weller 2021](#); [NCCN 2020](#)).

In accordance with the treatment guidelines, a recent study of AG-881, a dual IDH1/2 inhibitor, enrolled patients with gliomas (enhancing or non-enhancing disease) who have recurred or progressed following standard therapy OR have previously untreated disease ([NCT02481154](#)). This study enrolled 22 non-enhancing glioma patients, who had a median of 2 prior lines of treatment (range: 1-4). An objective response rate (ORR) of 13.6% was achieved, and 77.3% of patients achieved stable disease. At 24 months, 60.5% of patients were still alive, and progression free ([Mellinghoff 2020](#)). These study results showed encouraging preliminary activity with prolonged disease control, and reduced growth of non-enhancing tumors that warrants further exploration of IDH1/2 inhibitors in an underserved patient population.

Cohort D: Other Solid Tumors with an IDH1/2 Mutation

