4.2.1.5. Progression-free Survival

PFS is defined as the time (months) from the date of first administration of study treatment until the first radiographic documentation of objective progression as assessed by investigator using RECIST v1.1 or RANO criteria for glioma patients, or death from any cause.

More specifically, PFS will be determined using all the assessment data up until the last evaluable

visit prior to or on the date of

- (i) disease progression as defined by RECIST Version 1.1 or RANO or death; or
- (ii) withdrawal of consent or lost to follow-up; or
- (iii) receiving subsequent anti-cancer medication, whichever is earlier.

Patients without report of PD or death from any cause at the time of analysis are censored as described in [Table 5](#) below.

The PFS time will always be derived based on scan dates not tumor assessment dates. RECIST or RANO assessments/scans contributing towards a particular visit may be performed on different dates. The following rules are applied:

- Date of progression is determined based on the earliest of the dates of the component that triggered the progression.
- When censoring a patient for PFS, the patient is censored at the latest of the dates contributing to a particular overall visit assessment.

Table 5 Outcome and Event or Censoring Dates for PFS

Rule	Situation	Date of Progression or Censoring	Outcome
1	PD documented from radiological assessment visits	Date of first documented disease progression	Event
2	Death without PD or death after one missing radiological assessment visit	Date of death	Event
3	No baseline nor post-baseline radiological assessments available	Date of first administration of study treatment	Censored
4	No death or PD by the time of data cut-off for analysis	Date of last adequate radiological assessment	Censored
5	Early discontinuation (lost to follow-up or withdrawal of consent) of study without death or PD	Date of last adequate radiological assessment	Censored
6	New anti-tumor therapy started prior to PD	Date of last adequate radiological assessment prior to or on date of initiation of new therapy visit	Censored
7	Death or PD after two or more consecutive missed or inadequate radiological assessment visits	Date of last adequate radiological assessment prior to missed visits	Censored

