5.2.6. Prior and Subsequent Anti-cancer Therapy

Prior and subsequent anti-cancer therapy, including medication, radiotherapy, and procedure or surgery, will be summarized descriptively for the safety analysis set.

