5.2.6.1. Anti-cancer Medication

Prior anti-cancer medications are defined as those taken by the patient prior to the administration of study drug. Subsequent anti-cancer medications are defined as those taken by the patient after the discontinuation of the study drug.

Prior and subsequent anti-cancer medications will be coded to ATC therapeutic group (i.e. ATC Level 2) and PT using the WHO-DD Version Global B3 Sep 2024.

The prior anti-cancer medications will be summarized by presenting the number and percentage of patients by PT and ATC. Patients taking the same medication multiple times will only be counted once for that PT or ATC. Each summary will be ordered by descending order of incidence of ATC according to total column and PT within each ATC. If the frequencies tie, an alphabetic order will be applied.

Similarly, the subsequent anti-cancer medications will be summarized.

All prior and subsequent anti-cancer medications will be presented in a by-patient listing.

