5.2.6.3. Anti-cancer Procedure or Surgery

Prior anti-cancer procedure or surgery are defined as those taken by the patient prior to the administration of study drug. Subsequent anti-cancer procedure or surgery are defined as those taken by the patient after the discontinuation of the study drug.

Prior and subsequent anti-cancer procedure or surgery will be coded to SOC and PT using MedDRA 27.1 or higher.

The prior anti-cancer procedure or surgery will be summarized by presenting the number and percentage of patients by PT and ATC(i.e. ATC Level 2). Patients taking the same medication multiple times will only be counted once for that PT or ATC. Each summary will be ordered by descending order of incidence of ATC to total column and PT within each ATC. If the frequencies tie, an alphabetic order will be applied.

Similarly, the subsequent anti-cancer procedure or surgery will be summarized.

All prior and subsequent anti-cancer procedure or surgery will be presented in a by-patient listing.

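### Best overall response and the waterfall and spider plots stop at new anti-cancer medication but not at radiotherapy or surgery, so a scan after local therapy could be credited to HMPL-306 and could conflict with the duration-of-response censoring rule.

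*SAP*

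**What the plan says.** SAP 4.2.1.1 derives BOR from time point responses up to the earliest of three events. The first is progression or death, the second is withdrawal or loss to follow-up, and the third is "iii) receiving subsequent anti-cancer medications, whichever is earlier". SAP 5.2.9.1 applies the same three limits to the target-lesion data in the waterfall and spider plots. The paragraph that sets the data window for PFS in 4.2.1.5 also ends with "iii) receiving subsequent anti-cancer medication, whichever is earlier".

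Medication is only one of the classes the SAP recognises. Section 5.2.6 covers "Prior and subsequent anti-cancer therapy, including medication, radiotherapy, and procedure or surgery", and 5.2.6.1 to 5.2.6.3 define each class separately. In all three, *subsequent* means after study drug has stopped. For medication the text is "Subsequent anti-cancer medications are defined as those taken by the patient after the discontinuation of the study drug", and for surgery it is "Subsequent anti-cancer procedure or surgery are defined as those taken by the patient after the discontinuation of the study drug".

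The censoring tables use a broader trigger. Rule 6 in both Table 3 (DoR) and Table 5 (PFS) is "New anti-tumor therapy started prior to PD". In Table 5 the censoring date is "Date of last adequate radiological assessment prior to or on date of initiation of new therapy visit", and Table 3 is equivalent. The notes under both tables on same-day progression go back to medication.

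**The concern.** Resection removes the lesion being measured and radiotherapy can shrink it. If scans after such treatment stay in the BOR window, a CR, PR or MR due to local therapy can be counted as a drug response. The effect passes to every endpoint built on BOR: ORR, unconfirmed ORR, DCR, TTR, and the choice of patients who enter the DoR analysis. The best percentage change in the waterfall plot is exposed directly.

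There is also a conflict between endpoints. The DoR and PFS rules stop the same patient's follow-up at the new therapy. A patient can therefore be a responder on scans that the duration analysis does not accept.

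A smaller gap concerns timing. Local therapy given between the first and last dose, for example during a dose hold, is neither prior nor subsequent under 5.2.6, so a cut-off that depends on the word *subsequent* does not reach it.

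**Working it through.** The plan states no figure that depends on this rule, so there is nothing to reproduce. The check compares the rules and then uses arithmetic for scale.

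**1. The cut-offs side by side (SAP).**

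| Place | New-therapy trigger |
|---|---|
| 4.2.1.1 BOR, item (iii) | medication |
| 5.2.9.1 waterfall and spider plots, item (iii) | medication |
| 4.2.1.5 PFS data window, item (iii) | medication |
| Notes to Tables 3 and 5 | medication |
| Tables 3 and 5, rule 6; Tables 4 and 6 | any anti-tumor therapy |
| 4.1.3 safety treatment period | any anti-tumor therapy |

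**2. Can medication be read to include local therapy?** Not on the SAP's own terms. Medication is coded with the drug dictionary (5.2.6.1), radiotherapy is summarised by anatomical site (5.2.6.2), and procedures are coded in MedDRA (5.2.6.3). No other rule closes the BOR or plot window at radiotherapy or surgery.

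**3. How many scans does it take?**
- RANO (4.2.1.1, 4.2.1.2): one CR scan gives BOR of CR, and one MR scan can give MR. A single PR after SD is downgraded to MR, and MR counts in ORR by RANO. One scan is enough.
- Best percentage change (5.2.9.1): one scan is enough.
- RECIST: Table 2 maps SD followed by CR or PR to SD in both columns. A confirmed response needs two response scans at least 4 weeks apart. For the unconfirmed rate, one scan is enough only if no SD scan comes before it.

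**4. The conflict between endpoints.** Illustrative dates: SD at the week 8 scan (day 57), then local therapy, then a first response at week 16 (day 113) that qualifies for DoR (a RANO CR, or a RECIST response that is later confirmed). There is no progression.
- TTR (4.2.1.4) = (113 − 1 + 1)/30.4375 = 3.7 months.
- PFS is censored by rule 6 at day 57: (57 − 1 + 1)/30.4375 = 1.9 months.
- DoR is censored by rule 6 at day 57: (57 − 113 + 1)/30.4375 = −55/30.4375 = **−1.8 months**.

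The negative duration does not depend on these dates. It arises whenever the last scan on or before the local therapy is more than one day before the first response.

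**5. Scale for one misattributed responder.** The interval is the SAP's own two-sided 95% Clopper-Pearson: lower limit = Beta quantile(0.025; x, n − x + 1), upper limit = Beta quantile(0.975; x + 1, n − x), with the lower limit 0 when x = 0. Group sizes: 3 is the minimum per dose level and 12 the maximum extension (Protocol 4.1.1), 27 to 36 is all of Part 1 (SAP 2.3.1), and 6 is an intermediate case.

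| n | 0 responders | 1 responder |
|---|---|---|
| 3 | 0% (0 to 70.8) | 33.3% (0.8 to 90.6) |
| 6 | 0% (0 to 45.9) | 16.7% (0.4 to 64.1) |
| 12 | 0% (0 to 26.5) | 8.3% (0.2 to 38.5) |
| 27 | 0% (0 to 12.8) | 3.7% (0.1 to 19.0) |
| 36 | 0% (0 to 9.7) | 2.8% (0.1 to 14.5) |

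These rows assume that one affected patient exists. The documents do not say whether one does.

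**The case against.** The strongest reply is that such scans should hardly exist. Protocol 8.3.1 prohibits other cancer therapy on study, including radiotherapy. Protocol 6.2.1.1 requires discontinuation if other antitumor treatment is used. Efficacy follow-up scans end when new anticancer therapy starts (Protocol 6.1.20, repeated in SAP 2.2). Local therapy given because of documented progression is harmless here, since progression has already closed the window. This largely stands and sets the limit on the point. It does not remove it: tumor assessment runs through end of treatment (Protocol 6.1.13), discontinued patients are encouraged to attend the remaining visits (Protocol 6.2.1.1), and deviations happen. An analysis rule should not rely on the data being absent.

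A reader might infer that patients are likely to have local therapy before progression, because Protocol Appendix 11 says "Both EU and US guidelines recommend repeat surgery, alkylating chemotherapy re-irradiation, or experimental therapy". The documents do not support that. The sentence concerns treatment at recurrence, and it is part of the rationale for Cohort C, which enrolled nobody (SAP 1). Part 1 does admit gliomas (Protocol 5.2) and SAP 5.1.1 reports efficacy by glioma grade, so the RANO route is open, but its frequency is unknown.

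A reader might also infer that post-local-therapy scans count in PFS. They do not: 4.2.1.5 computes PFS from the Table 5 dates, and rule 6 censors at new anti-tumor therapy. Nor is medication the only limit on BOR, since progression, death, withdrawal and loss to follow-up also close the window.

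Finally, the SAP uses its terms loosely and never defines anti-tumor therapy. That is true, but 5.1.2.6 uses it interchangeably with anti-cancer therapy, which 5.2.6 says includes all three classes. If rule 6 were instead read as medication only, the conflict would disappear, but only because the gap would then extend to DoR and PFS.

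**Conclusion.** The point holds for BOR, the endpoints derived from it, and the waterfall and spider plots. Among new therapies, the written cut-off names medication alone, so a scan after radiotherapy or resection given without documented progression could be counted as an effect of HMPL-306. The same patient could then have DoR censored before the response begins. For PFS there is only a wording mismatch with the operative Table 5 rule.

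Exposure is confined to off-schedule, end-of-treatment or protocol-deviation scans. It is greatest for RANO CR and MR and for best percentage change, where one scan decides the result. The size is conditional: one such patient moves ORR by 33 percentage points in a group of 3, and by about 3 to 4 points across 27 to 36 subjects. ORR is secondary and no hypothesis is tested, so no sample size or error rate changes. The conclusion rests on reading the SAP's therapy classes as 5.2.6 defines them, and on the conduct rules in the protocol version reviewed (Amendment 2; the SAP cites Amendment 3).

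**What to change.** Define one term and use it throughout: *new anti-cancer therapy (medication, radiotherapy, or anti-cancer procedure or surgery) started after the first dose of study drug, whether before or after its discontinuation*. Put it in:

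- item (iii) of 4.2.1.1 and item (iii) of 5.2.9.1, where the result can change;
- item (iii) of 4.2.1.5 and the same-day notes to Tables 3 and 5, for consistency;
- rule 6 of Tables 3 and 5, so that the censoring trigger is defined by the same words.

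Section 5.1.2.6 should be checked against the new term, because it moves an imputed therapy date that falls before the last dose to the day after it.

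The cost is SAP wording and the matching programming. All three classes are already listed by patient under 5.2.6, and procedures during treatment are captured under 5.2.8. The downside is that a response first seen only after local therapy is no longer counted. It would still appear in the tumor evaluation listings.
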